# The participant will be requested to maintain a medication diary. The medication diary and empty pill containers will be returned to clinic staff at the end of each cycle.

Stem cell collection using standard mobilization procedures of the Institute can be performed for patients who are eligible and will be performed at the time of best remission or after 9 cycles of therapy. Patients may delay treatment for up to 3 weeks after stem cell collection is complete.

During maintenance, patients may return to clinic every 3 cycles beginning with cycle 10. If this option is utilized, a 3-month supply of ixazomib will be supplied by the investigational pharmacy at each visit. Lenalidomide may be shipped from the investigational pharmacy to the patient's home for each cycle the patient does not return to clinic, according to local practice.

#### 5.2 Agent Administration

The order in which the drugs are administered does not matter.

#### 5.2.1 Ixazomib

The ixazomib drug product is provided in strengths of 4.0-, 3.0-, and 2.3-mg and 2.0-, 0.5-, and 0.2 mg capsules as the active boronic acid. The different dose strengths are differentiated by both capsule size and color as described in table 9 below:

| Dose     | Capsule Size | Capsule Color |  |
|----------|---------------------|----------------------|--|
| Strength |                     |                      |  |
| 4.0 mg   | Size 4              | Ivory                |  |
| 3.0 mg   | Size 3              | Light gray           |  |
| 2.3 mg   | Size 2              | Light pink           |  |
| 2.0 mg   | Size 2              | Swedish orange       |  |
| 0.5 mg   | Size 3              | Dark green           |  |
| 0.2 mg   | Size 4              | White opaque         |  |

#### Table 9: Ixazomib Capsule Description

For additional details, please see the ixazomib IB.

For more detailed information regarding ixazomib product information please refer to Section 8.1.

All protocol-specific criteria for administration of study drug must be met and documented before drug administration. Study drug will be administered or dispensed only to eligible patients under the supervision of the investigator or identified subinvestigator(s). Patients should be monitored for toxicity, as necessary, and doses of ixazomib should be modified as needed to accommodate patient tolerance to treatment; this may include symptomatic treatment, dose interruptions, and adjustments of ixazomib dose (see Section 6.1).

Capsules of ixazomib will also be referred to as study drug. Study drug will be supplied by Millennium as capsules of 2.3, 3.0 and 4.0 mg ixazomib. The prescribed administration of ixazomib doses in this study is 4 mg ixazomib in a 28-day cycle.

Missed doses can be taken as soon as the patient remembers if the next scheduled dose is 72 hours or more away. A double dose should not be taken to make up for a missed dose. If the patient vomits after taking a dose, the patient should not repeat the dose but should resume dosing at the time of the next scheduled dose.

#### 5.2.1.1 Dose Delay or Interruption

Please refer to section 6.1 of the protocol

#### 5.2.2 Lenalidomide

Lenalidomide will be given as a single daily oral dose of 25 mg per day on days 1–21 followed by a 7-day rest period for cycles 1–9 and 15 mg per day on days 1-21 for cycles 10–24. A window of +/-7 days is allowed, except cycles 1 and 2 which will be +/-3 days. Dose modification guidelines are described in Section 6.2 (Dose Modifications/Delays).

Lenalidomide capsules should be swallowed whole, and should not be broken, chewed or opened. Administration of lenalidomide will be at approximately the same time each day. Drug may be taken with or without food. If a dose is missed and less than 12 hours has elapsed since the missed dose, the patient can take the dose for that day. If more than 12 hours has elapsed since missing a dose at the normal time, the patient should not take the dose, but take the next dose at the normal time on the following day. If a dose is missed, it should be taken as soon as possible on the same day. If a dose is vomited, the dose should not be made up and the participant should continue with the regular schedule of the drug at the next dose. A drug diary will be provided to participants to record oral administration of doses.

Participants who take more than the prescribed dose of lenalidomide should be instructed to seek emergency medical care if needed and contact study staff immediately. Participants experiencing adverse events may need study treatment modifications (see Section 6.2).

Lenalidomide related resources will be provided to all patients prior to receiving lenalidomide therapy as part of the Revlimid REMS program. For more information regarding program registration and drug ordering, refer to section 8.2.

5.2.2.1 Dose Delay or Interruption

Please refer to sections 6.1 and 6.2 of the protocol.

#### 5.2.3 **Dexamethasone**

Dexamethasone will be obtained from commercial supply in this study. This may lead to added costs for the participant or the participant's insurance company.

Dexamethasone will be given as a single oral dose on days 1, 8, 15, and 22 of each 28 day cycle during the induction phase of this study (Cycles 1-9 only).

Dexamethasone should be taken at approximately the same time each day. It is recommended that dexamethasone be taken in the morning to reduce insomnia. Each dose should be taken with food. If a dose of dexamethasone is vomited, the participant should continue with the regular schedule of the drug at the next dose. If a dose is missed and less than 12 hours has elapsed since the missed dose, the patient may take the dose for that day. If more than 12 hours has elapsed since missing a dose at the normal time, the patient should not take the dose, but take the next dose at the normal time on the following day. A drug diary will be provided to participants to record oral administration of doses.

At the treating investigator's discretion, dexamethasone may be given as a split dose over 2 consecutive days.

#### 5.2.3.1 Dose Delay or Interruption

Please refer to section 6.3 of the protocol.

Dose modification guidelines are described in Section 6.3 (Dose Modifications/Delays).

#### 5.3 General Concomitant Medication and Supportive Care Guidelines

5.3.1 Medications and supportive care

- Patients who experience worsening neuropathy from baseline may be observed for recovery, and have dose reductions/delays as indicated in the protocol, and any supportive therapy or intervention may be initiated as appropriate at the discretion of the investigator.
- Supportive measures consistent with optimal patient care may be given throughout the study.
- Stem cell mobilization will be allowed at the time of best response or at the end of induction therapy (after 9 cycles) for patients who are eligible for stem cell transplant. Standard mobilization treatment (with GCSF or with cyclophosphamide or plerixafor, etc) will be used based on Institutional guidelines. Patients may delay treatment for up to 6 to 8 weeks for mobilization purposes. Filgrastim is allowed per standard protocol for stem cell mobilization if stem cell mobilization will be performed. This will be allowed per standard procedure of stem cell collection per

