#### 2.13 Trial Rationale

Based on the activity of lenalidomide and dexamethasone in patients with SMM and based on the safety and activity profile of Ixazomib/len/dex in patients with untreated MM (ASH 2014), we propose to examine in a phase II trial the activity of ixazomib/lenalidomide/dexamethasone (IRD) in patients with high-risk smoldering MM.

Patients who develop symptomatic disease will receive induction therapy with standard therapeutic options for multiple myeloma including combinations such as those of proteasome inhibitors, immunomodulators and steroids or cyclophosphamide, proteasome inhibitors and dexamethasone.

Patients who are eligible for stem cell collection will have the option to collect stem cells during the course of therapy on this trial at the time of best response (CR or VGPR) or after 9 cycles of induction therapy. If we observe any problems with stem cell collection, we will follow the current standard guidelines of using cyclophosphamide or plerixafor mobilization. Based on data using combination therapies for induction, there has been no major concerns regarding stem cell collections after treatment with those agents.

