## Treatment may not begin without confirmation from the Coordinating Center that the participant has been registered.

### NOTE: Same day treatment registrations will only be accepted with prior notice and discussion with DFCI.

#### 5. TREATMENT PLAN

#### 5.1 Treatment Regimen

Treatment will consist of 9 cycles of induction therapy followed by maintenance therapy for a total of 24 months. A treatment cycle is defined as 28 consecutive days.

For treatments cycle 1 and 2, a +/- 3 day window is allowed. For treatments cycle 3 through 24 a +/-7 day window is allowed.

No investigational or commercial agents or therapies other than those described below may be administered with the intent to treat the participant's malignancy.

| Agent         | Pre-medications/
Precautions                              | Dose  | Route | Schedule                   | Cycle
Length |
|---------------|--|-------|-------|----------------------------|-----------------|
| Ixazomib      | Should not be taken with food                                | 4 mg  | Oral  | Days 1, 8, 15              |                 |
| Lenalidomide  | None   | 25 mg | Oral  | Days 1–21 of
each cycle | 28 days         |
| Dexamethasone | Take with food;
Recommended to be
taken in the morning | 40 mg | Oral  | Days 1, 8, 15, 22          | -               |

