- Systemic treatment with any of the following metabolizing enzyme inducers should be avoided, unless there is no appropriate alternative medication for the patient's use (Rationale: If there were to be a DDI with an inducer, ixazomib exposure would be less; therefore, there would be a reduced chance of an AE. However, there may be less chance for an antitumor effect, but that is not an absolute reason to be taken off ixazomib):
  - Strong CYP3A inducers: rifampin, rifapentine, rifabutin, carbamazepine, phenytoin, and phenobarbital
  - Excluded foods and dietary supplements include St. John's Wort and Ginkgo Biloba
- The following procedures are prohibited during the study.
  - Any antineoplastic treatment with activity against MM, other than study drugs
  - Radiation therapy (note that, in general, the requirement for local radiation therapy indicates disease progression)

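### Cyclophosphamide mobilization is both allowed and barred in section 5.3, and for patients who collect after cycle 9 the end-of-induction assessment falls by default after it, with no rule for how CR, VGPR and MRD then count

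*Combined protocol and SAP*

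**What the plan says.** **Permission.** Section 5.3 lets transplant-eligible patients mobilize at best response or after nine cycles: "Standard mobilization treatment (with GCSF or with cyclophosphamide or plerixafor, etc) will be used based on Institutional guidelines".

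**Prohibition.** The list of prohibited procedures that closes section 5.3 includes "Any antineoplastic treatment with activity against MM, other than study drugs". It has no exception for mobilization. Section 5.1 is narrower: no other agent "may be administered with the intent to treat the participant's malignancy".

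**Rationale.** Section 2.13 names cyclophosphamide within the standard options for patients who develop symptomatic disease; that list ends "steroids or cyclophosphamide, proteasome inhibitors and dexamethasone". On mobilization it says: "If we observe any problems with stem cell collection, we will follow the current standard guidelines of using cyclophosphamide or plerixafor mobilization". Cyclophosphamide or plerixafor is there the answer to a problem, whereas section 5.3 lists both as ordinary options.

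**Delay.** Section 5.1: "Patients may delay treatment for up to 3 weeks after stem cell collection is complete". Section 5.3: "Patients may delay treatment for up to 6 to 8 weeks for mobilization purposes".

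**Assessments.** The section 10 calendar puts the marrow at Cycle 10 Day 1 or at confirmation of CR. M-protein and free light chain tests are on Day 1 of cycles 1 to 9 and then every three months, with maintenance visits starting at cycle 10. Appendices B and C treat the end of cycle 9 and Cycle 10 Day 1 as one time point. Footnote 8 waives a repeat marrow if one was done within 3 weeks of Cycle 10 Day 1, or if a CR-confirming marrow was done within 3 weeks of stem-cell collection. Section 9 ties MRD to reaching CR or VGPR.

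**Analysis.** Section 11.2.3.1 counts a response only on assessments that precede any new therapy, and does not classify mobilization. Section 13.1.2 reports response and MRD proportions with 90% exact intervals and has no rule for mobilized patients. Section 11.2.7 plans no central review of response.

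**The concern.** Response and MRD are secondary objectives of a single-arm trial, so no control group receives the same co-intervention. If a patient is given a non-study cytotoxic that the protocol itself lists in a myeloma regimen, and the depth of response is measured only afterwards, any improvement is reported as the effect of ixazomib, lenalidomide and dexamethasone.

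The regimen follows institutional guidelines, so exposure can differ between sites. Because mobilization is unclassified and response is not reviewed centrally, two sites could score the same case differently. One could treat cyclophosphamide as new therapy and stop counting. The other could treat it as supportive care and carry on.

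**Working it through.** **1. The plan's own figure.** Section 13.1 gives 53 eligible patients, a 50% null rate, a 70% alternative, type I error 0.05 and power 0.91. With success at 33 or more of 53:
- P(X ≥ 33 | n = 53, p = 0.5) = 0.0492
- P(X ≥ 33 | n = 53, p = 0.7) = 0.914
- 53 / 0.95 = 55.8, rounded up to 56

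These reproduce the plan. Nothing below changes them.

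**2. The text side by side.** The permission in 5.3 names cyclophosphamide. The prohibition in 5.3 covers any non-study antineoplastic active against myeloma, without regard to why it is given. Section 2.13 supplies the link, because it places cyclophosphamide in a myeloma regimen. Only 5.1 refers to intent, and the prohibition in 5.3 does not repeat that limit.

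**3. Timing for a patient who collects after cycle 9.** Inputs: 28-day cycles (section 1.4), the delays in 5.1 and 5.3, and the 3-week window in footnote 8. Cycle 9 ends on day 9 × 28 = 252. For a delay of d weeks, Cycle 10 Day 1 is day 253 + 7d, and the earliest marrow in the window is 21 days before that.

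| Delay d (weeks) | Cycle 10 Day 1 | Earliest qualifying marrow | Relative to end of cycle 9 |
|---|---|---|---|
| 0 | day 253 | day 232 | 20 days before |
| 3 | day 274 | day 253 | 1 day after |
| 6 | day 295 | day 274 | 22 days after |
| 8 | day 309 | day 288 | 36 days after |

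With the delay in 5.3, a marrow taken as cycle 9 ends does not qualify under the Cycle 10 Day 1 limb. Adding the 7-day visit window to the 3 weeks does not rescue it: the earliest days become 274 − 7 = 267 and 288 − 7 = 281, still 15 and 29 days after cycle 9 ends. If the full 3 weeks after collection in 5.1 is used, the window opens only on the day collection is complete.

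The other limb of footnote 8 covers only a CR-confirming marrow and does not say whether it must come before or after collection. For blood tests, the last scheduled Day 1 before mobilization is Cycle 9 Day 1, day 8 × 28 + 1 = 225. The next is Cycle 10 Day 1, which is 295 − 225 = 70 days later with a 6-week delay and 309 − 225 = 84 days later with an 8-week delay.

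**4. Size.** Each reclassified patient moves a proportion by 1/n. For n = 56 this is 1/56 = 1.8 points. MRD has a smaller base: section 11.2.4 measures it in Dana-Farber patients at VGPR or better, and 11.2.4.1 drops those without a high-frequency clone. If 20 to 40 patients were measured (an assumption), the step would be 1/40 = 2.5 to 1/20 = 5.0 points.

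The documents give neither the share mobilized with cyclophosphamide nor its effect on response category. As an assumption only, exposure of 10% to 50% and upgrading in 10% to 30% of those exposed give 0.10 × 0.10 = 1 point to 0.50 × 0.30 = 15 points. For scale, the 90% exact interval for 28/56 runs from 38.3% to 61.7%.

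**The case against.** The best case for the plan has four parts.

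**A specific permission normally governs a general bar**, and 5.1 frames its own restriction by intent to treat. That is a likely reading of what was meant. But the prohibition in 5.3 carries no intent limit and no text states an exception, so a site could read it either way.

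**Many patients are already assessed.** Section 2.13 places best-response collection at CR or VGPR, and MRD is triggered then. M-protein and free light chain through Cycle 9 Day 1 precede any mobilization after cycle 9. This stands and narrows the point. A reader might infer that the end-of-induction assessment always follows cyclophosphamide. The documents do not support that: it is the default only for patients who collect after cycle 9, and a short delay can leave an earlier marrow inside the window.

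**The size is unknown.** This also stands. Section 2.13 presents cyclophosphamide or plerixafor as a fallback, and G-CSF is an alternative in 5.3. No particular inflation can be claimed.

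**Later deepening is expected from study drug.** A reader might conclude that best response should be scored only before cyclophosphamide. That would discard up to 15 maintenance cycles of study treatment. In the phase 3 trial described in section 2.6, PR or better rose from 79% after induction to 90% during maintenance. The restriction belongs in a sensitivity analysis.

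The two delay limits might also look contradictory. One runs from completed collection and the other covers mobilization as a whole, so both can hold. What is missing is a statement of how they relate.

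**Conclusion.** The concern holds for a subset: transplant-eligible patients who collect after cycle 9 and receive cyclophosphamide. For them the end-of-induction marrow and blood tests fall by default after a non-study drug, and no rule says how those results count. CR or VGPR depth and MRD are the exposed endpoints. Patients who collect at best response are less exposed, though a VGPR that later becomes CR also follows the extra drug.

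A reader might infer that the overall response rate or the sample size is compromised. Neither follows. PR or better is little affected, because best-response collectors are already past it and serum response through Cycle 9 Day 1 is on record. The design figures reproduce unchanged.

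The firm number is 1.8 points per reclassified patient on a base of 56, and more for MRD on its smaller base. The 1 to 15 point range rests wholly on assumed exposure and upgrading. This is an inexpensive improvement to secondary endpoints.

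**What to change.** - **Section 10 calendar.** For patients who mobilize, take the already planned end-of-induction or CR marrow, with its MRD sample, and the M-protein and free light chain tests before the first mobilization drug. Amend footnote 8 so that this marrow replaces the Cycle 10 Day 1 marrow whatever the length of the mobilization delay.
- **Case report form.** Record mobilization regimen and date.
- **Section 11.2.3.1.** State whether mobilization cyclophosphamide counts as new therapy.
- **Section 13.1.2.** Keep best response over the whole treatment period as the main analysis. Add a sensitivity analysis of CR/VGPR and MRD that uses only pre-cyclophosphamide assessments for exposed patients. Give the denominator for the MRD proportion.
- **Sections 5.3, 2.13 and 5.1.** Reconcile the permission in 5.3 with the prohibition in 5.3 and with the fallback wording in 2.13, and say how the delay limits in 5.1 and 5.3 relate. Which clinical rule applies is for the sponsor; none is proposed here.

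The cost is amendment wording, one or two form fields, and an existing marrow moved earlier by days to weeks. If the Cycle 10 Day 1 blood tests are also kept, it adds at most one blood draw.

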#### Institutional guidelines.

- Use of white cell growth factors [Filgrastim or acceptable equivalent] is allowed • for management of treatment induced neutropenia at physician discretion. Filgrastim should be given according to the ASCO guidelines. Pegfilgrastim is not to be used in replace of filgrastim.
- Patients should be transfused with red cells and platelets as clinically indicated and according to institutional guidelines.
- Patients will receive bisphosphonates per recommendations of myeloma therapy. • A note will be placed about patients who are not receiving bisphosphonates for clinical reasons such as osteonecrosis of the jaw.
- Nausea/Vomiting: If nausea and/or vomiting is noted at any point in time, premedication with prochlorperazine or other antiemetics may be used before future doses. Antiemetics, including 5-HT3 serotonin receptor antagonists, may be used as needed at the discretion of the investigator.
- If nausea persists in spite of the use of standard antiemetics additional symptom management should be as per standard antiemetic guidelines.
- Diarrhea: Loperamide or other antidiarrheal should be used for symptomatic • diarrhea at discretion of the investigator. The dose and regimen will be according to institutional guidelines. IVF should be given to prevent volume depletion.
- Thromboprophylaxis is required for all participants. Participants may receive • daily aspirin administration (81 or 325 mg), daily enoxaparin (40 mgs), or low molecular weight heparin (type Innohep® 4500 UI anti-Xa as needed) or equivalent to decrease the risk of thromboembolic complications. Aspirin prophylaxis will be the preferred first choice unless contraindicated. It is recommended that if the platelet count falls below 30,000/mm3, thromboprophylaxis be held to minimize the risk of bleeding and then resumed when platelet counts are equal to or above this level.
- Nonsteroidal anti-inflammatory drugs (NSAIDs) should be avoided with • impaired renal function given reported NSAID-induced renal failure in patients with decreased renal function.
- Prophylaxis Against Risk of Reactivation of Herpes Infection virus: Patients may be at an increased risk of infection including reactivation of herpes zoster and herpes simplex viruses. Antiviral therapy such as acyclovir, valacyclovir, or other

antivirals may be initiated as clinically indicated at the discretion of the treating investigator. Other antivirals are also acceptable.

- Systemic treatment with any of the following metabolizing enzyme inducers should be avoided, unless there is no appropriate alternative medication for the patient's use (Rationale: If there were to be a DDI with an inducer, ixazomib exposure would be less; therefore, there would be a reduced chance of an AE. However, there may be less chance for an antitumor effect, but that is not an absolute reason to be taken off ixazomib):
  - Strong CYP3A inducers: rifampin, rifapentine, rifabutin, carbamazepine, phenytoin, and phenobarbital
  - Excluded foods and dietary supplements include St. John's Wort and Ginkgo Biloba
- The following procedures are prohibited during the study.
  - Any antineoplastic treatment with activity against MM, other than study drugs
  - Radiation therapy (note that, in general, the requirement for local radiation therapy indicates disease progression)

